6.3.2.2 Supportive therapies for AEs Suspected to Be Related to Pembrolizumab

Example supportive therapies for managing AEs, which may be immunological etiology suspected to be related to pembrolizumab, are presented below. For the details, see the guidance document on events of special interest. A reduction in the corticosteroid dose may

exacerbate symptoms; thus, attention should be paid that administration of corticosteroid as tapering the dose for a few cycles will be required. An additional supportive therapy may be needed so that an effort shall be made to eliminate other causes of disease such as metastatic lesions and bacterial or viral infections for each symptom.

Pneumonitis:

In case of Grade 2, systemic corticosteroid should be administered. If the symptom recovered to Grade 1 or lower, the corticosteroid dose should be tapered over 4 or more weeks.

In case of Grade 3 to 4, treatment with intravenous corticosteroid should be immediately administered. As necessary, an anti-inflammatory agent should be additionally administered. If the duration of corticosteroid treatment is extended, an antibiotic should be additionally administered to prevent opportunistic infection.

Diarrhoea/Colitis:

Whether or not there is any sign or symptom of enterocolitis (e.g., whether or not being accompanied by diarrhoea, abdominal pain, bloody or mucous stools, or pyrexia) and sign or symptom of bowel perforation (signs of peritonitis or intestinal obstruction) should be checked.

All patients who developed diarrhoea/colitis should be instructed to take a sufficient amount of water. If it is difficult to take a sufficient amount of water, water containing electrolytes should be intravenously administered. In case of \geq Grade 2 diarrhoea, consultation with a gastroenterologist and endoscopy are recommended for confirming or denying colitis.

In case of Grade 2 diarrhoea/colitis persisting for more than 3 days, oral corticosteroid should be administered.

In case of Grade 3 to 4 diarrhoea/colitis persisting for more than one week, intravenous corticosteroid followed by high-dose oral corticosteroid should be administered.

If the symptom recovered to Grade 1 or lower, the corticosteroid dose should be tapered over 4 or more weeks.

Type 1 diabetes mellitus [if newly occurred, including diabetic ketoacidosis (DKA)], and \geq Grade 3 hyperglycaemia with ketosis (ketonuria) or metabolic acidosis (DKA):

For type 1 diabetes mellitus, and Grade 3 to 4 hyperglycaemia with metabolic acidosis or ketonuria, insulin replacement therapy should be considered.

Serum glucose levels and metabolic laboratory values (urine ketone, glycohemoglobin and C-peptide) should be assessed.

Hypophysitis:

In case of Grade 2, corticosteroid should be administered. If the symptom recovered to Grade 1 or lower, the corticosteroid dose should be tapered over 4 or more weeks. Since corticosteroid is administered as tapering the dose, appropriate hormone replacement therapy may be required.

In case of Grade 3 to 4, intravenous corticosteroid followed by oral corticosteroid should be administered. If the symptom recovered to Grade 1 or lower, the corticosteroid dose should be tapered over 4 or more weeks. Since corticosteroid is administered as tapering the dose, appropriate hormone replacement therapy may be required.

Hyperthyroidism and hypothyroidism:

Thyroid dysfunction may occur at any time during dosing. Whether or not there is any change in thyroid function test values (Conduct at the start of the administration of the investigational drug, thereafter periodically and as necessary based on clinical evaluation.) and sign or symptom of thyroid dysfunction should be observed.

Grade 2 hyperthyroidism (and Grade 3 to 4 hypothyroidism):

For hyperthyroidism, non-selective β blockers (e.g., propranolol) are recommended as first-line drugs.

For hypothyroidism, thyroid-hormone replacement therapy with levothyroxine or liothyronine is recommended as standard therapy.

Grade 3 to 4 hyperthyroidism:

Intravenous corticosteroid followed by oral corticosteroid should be administered. If the symptom recovered to Grade 1 or lower, the corticosteroid dose should be tapered over 4 or more weeks. Since corticosteroid is administered as tapering the dose, appropriate hormone replacement therapy may be required.

Liver:

In case of Grade 2, liver function tests should be performed frequently until values returned to baseline levels (Consider implementing the test every week.).

Intravenous or oral corticosteroid should be administered.

In case of Grade 3 to 4, intravenous corticosteroid should be administered over 24 to 48 hours.

If the symptom recovered to Grade 1 or lower, the corticosteroid dose should be tapered over 4 or more weeks.

Renal failure or nephritis:

In case of Grade 2, corticosteroid should be administered.

In case of Grade 3 to 4, corticosteroid treatment should be given.

If the symptom recovered to Grade 1 or lower, the corticosteroid dose should be tapered over 4 or more weeks.

Management of infusion reactions: Signs or symptoms of infusion reactions usually appear during or immediately after drug administration and often completely resolve within 24 hours postdose.

Actions to be taken if infusion reactions to pembrolizumab occurred are presented in Table 6.3.2.2

In the case where systemic corticosteroid treatment is judged to be necessary for immune-related Grade 2 or \geq 3 toxicities other than those mentioned above upon discussion with the coordinating committee, the treatment should be administered. If the symptom recovered to Grade 1 or lower, the corticosteroid dose should be tapered over 4 or more weeks.

Table 6.3.2.2. Actions to be taken if infusion reactions to pembrolizumab occurred

NCI CTCAE Grade	Action	Pretreatment from the next dosing
Grade 1 Mild reaction; not requiring infusion interruption or treatment.	Vital signs should be more frequently monitored until the patient's symptom become stable at the discretion of the investigator.	None
Grade 2 Requiring infusion interruption, but immediately responding to symptomatic treatment (e.g., antihistamines, nonsteroidal anti-inflammatory drugs (NSAIDs), narcotic analgesics, and intravenous infusion); requiring prophylactic treatment within 24 hours.	
Pembrolizumab infusion should be interrupted, and the symptom should be monitored.
 
An appropriate therapeutic action (e.g., administration of intravenous infusion, antihistamines, NSAIDs, acetaminophen and narcotic analgesics) should be taken.
 
Vital signs should be more frequently monitored until the patient's symptom become stable at the discretion of the investigator.
 
If the symptom resolved within one hour after treatment interruption, the treatment should be resumed at an infusion rate 50% slower than the original rate (e.g., from 100 mL/hr to 50 mL/hr).
 
If the symptom does not resolve within one hour after treatment interruption, the treatment should be discontinued until
	
Pretreatment with the following drugs should be given 1.5 hours (\pm 30 minutes) before pembrolizumab infusion:
 
Oral administration of diphenhydramine 50 mg (or equivalent antihistamine)
 
Oral administration of acetaminophen 500 to 1000 mg (or equivalent antipyretic)

	
the symptom resolves. Pretreatment should be given at the next dosing.
 
Pembrolizumab therapy should be discontinued in patients who developed Grade 2 toxicity despite appropriate pretreatment (reintroduction prohibited).
	

Grade 3 Prolongation (not quickly respond to symptomatic treatment or infusion interruption for a short period of time); recurring after improvement; and sequelae (e.g., renal disorder and lung infiltration) requiring hospitalization.
 
Grade 4 Life-threatening; and requiring treatment with a hypertensive drug or artificial respiration
	
Pembrolizumab infusion should be interrupted. An appropriate therapeutic action (e.g., administration of intravenous infusion, antihistamines, NSAIDs, acetaminophen, narcotic analgesics, oxygen inhalation, hypertensive drugs, corticosteroids and epinephrine) should be taken.
 
Vital signs should be more frequently monitored until the patient's symptom become stable at the discretion of the investigator.
 
The patient should be admitted to the hospital as necessary.
 
Pembrolizumab therapy should be discontinued (reintroduction prohibited).
	Pembrolizumab should not be resumed.
During pembrolizumab infusion, an appropriate resuscitation device should be placed in the room so that the physician can promptly take an action.		

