6.3.2. Criteria for Changes in Pembrolizumab therapy

6.3.2.1 Dose modification of Pembrolizumab

For AEs (whether serious or non-serious) related to pembrolizumab exposure, immunological factors may be involved. Such AEs may occur immediately after the start of investigational drug administration or several months after the last dose. For toxicity and

severe or life-threatening AEs related to pembrolizumab, pembrolizumab therapy should be interrupted or discontinued in accordance with Table 6.3.2.1.

Table 6.3.2.1. Dose modification of Pembrolizumab

General instructions:			
Immune-related AEs	Toxicity grade or conditions (CTCAEv4.0)	Action taken to pembrolizumab	Monitor and follow-up
Pneumonitis	Grade 2	Withhold	
 Monitor participants for signs and symptoms of pneumonitis Evaluate participants with suspected pneumonitis with radiographic imaging and initiate corticosteroid treatment Add prophylactic antibiotics for opportunistic infections
	Grade 3 or 4, or recurrent grade 2	Permanently discontinue	
Diarrhea / colitis	Grade 2 or 3	Withhold	
 Monitor participants for signs and symptoms of enterocolitis (i.e. diarrhea, abdominal pain, blood or mucus in stool with or without fever) and of bowel perforation (i.e. peritoneal signs and ileus). Participants with \geq Grade 2 diarrhea suspecting colitis should consider GI consultation and performing endoscopy to rule out colitis.
	Grade 4	Permanently discontinue	

			
 Participants with diarrhea/colitis should be advised to drink liberal quantities of clear fluids. If sufficient oral fluid intake is not feasible, fluid and electrolytes should be substituted via IV infusion.
AST / ALT elevation or Increased Bilirubin	Grade 2	Withhold	
 Monitor with liver function tests (consider weekly or more frequently until liver enzyme value returned to baseline or is stable)
	Grade 3 or 4	Permanently discontinue	
Type 1 diabetes mellitus (T1DM) or Hyperglycemia	Newly onset T1DM or Grade 3 or 4 hyperglycemia associated with evidence of β -cell failure	Withhold	
 Monitor participants for hyperglycemia or other signs and symptoms of diabetes.
Hypophysitis	Grade 2	Withhold	
 Monitor for signs and symptoms of hypophysitis (including hypopituitarism and adrenal insufficiency)
	Grade 3 or 4	Withhold or permanently discontinue ¹	

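### For diarrhoea/colitis, the written wait before corticosteroid is longer at Grade 3–4 (more than one week) than at Grade 2 (more than 3 days)

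*Combined protocol and SAP*

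**What the plan says.** The diarrhoea/colitis entry in section 6.3.2.2 gives two corticosteroid triggers in consecutive sentences. The first is "In case of Grade 2 diarrhoea/colitis persisting for more than 3 days, oral corticosteroid should be administered". The second covers the higher grades: "Grade 3 to 4 diarrhoea/colitis persisting for more than one week, intravenous corticosteroid followed by high-dose oral corticosteroid should be administered".

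The pneumonitis entry in the same section runs the other way, with urgency rising with grade: "In case of Grade 3 to 4, treatment with intravenous corticosteroid should be immediately administered".

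The section qualifies its own status. It opens with "Example supportive therapies for managing AEs, which may be immunological etiology suspected to be related to pembrolizumab, are presented below", then adds "For the details, see the guidance document on events of special interest". It also asks that "an effort shall be made to eliminate other causes of disease such as metastatic lesions and bacterial or viral infections for each symptom".

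Other measures for diarrhoea/colitis depend on grade alone. From Grade 2 upward, "consultation with a gastroenterologist and endoscopy are recommended for confirming or denying colitis". Under section 6.3.2.1, "pembrolizumab therapy should be interrupted or discontinued in accordance with Table 6.3.2.1"; that table withholds pembrolizumab at Grade 2 or 3 and stops it permanently at Grade 4.

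**The concern.** A reader expects the threshold for corticosteroid to fall, or at least not rise, as the event becomes more severe. Here the treatment is stronger at Grade 3–4 but the wait before it is longer. A site following the sentence literally could start corticosteroid later in a patient who deteriorates quickly than in one whose diarrhoea stays at Grade 2.

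Attribution adds to the difficulty. The lenvatinib dose-modification table in section 6.3.1.1 (footnote a) lists diarrhoea among the events to manage medically before lenvatinib is interrupted or reduced. The cause may therefore be unclear at onset, which makes clear corticosteroid timing more useful. What is at stake is patient safety. The response-rate endpoint, the sample size and the two-stage decision rule are not involved.

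**Working it through.** The check compares the two triggers, sets the entry beside the others in its section, and looks elsewhere in the protocol for an earlier start.

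**1. Does the Grade 2 trigger also cover Grade 3–4?** On its wording, no. The sentence just before it, on consultation and endoscopy, applies to Grade 2 and above. The corticosteroid sentence names Grade 2 only. The group left without an early trigger is therefore patients who reach Grade 3–4 within the first 3 days.

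**2. Size of the gap.** Inputs from section 6.3.2.2: Grade 2 threshold 3 days; Grade 3–4 threshold one week, or 7 days. Let k be the days spent at Grade 2 before reaching Grade 3–4, with k from 0 to 3. The text does not say when the week starts, so both readings are shown.

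- Week counted from onset of diarrhoea: gap = 7 − 3 = 4 days, for every k.
- Week counted from reaching Grade 3–4: gap = (k + 7) − 3 = k + 4 days.

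| k (days at Grade 2 first) | Gap, week from onset | Gap, week from Grade 3–4 | Days from onset to trigger, week from Grade 3–4 |
|---|---|---|---|
| 0 | 4 | 4 | 7 |
| 1 | 4 | 5 | 8 |
| 2 | 4 | 6 | 9 |
| 3 | 4 | 7 | 10 |

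The inversion holds under both readings. These are differences between written thresholds, not measured delays in care.

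**3. The other entries in 6.3.2.2.** Six events carry their own Grade 3–4 corticosteroid instruction (the infusion-reaction table and the closing provision for other toxicities are not counted):

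| Event | When corticosteroid starts at Grade 3–4 |
|---|---|
| Pneumonitis | Immediately |
| Diarrhoea/colitis | After more than one week |
| Hypophysitis | No start time given |
| Hyperthyroidism | No start time given |
| Liver | No start time given |
| Renal failure or nephritis | No start time given |

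One of six has a persistence condition. The 24 to 48 hours in the liver entry describes the period of administration, not a wait.

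**4. Is there an earlier start elsewhere?**

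- Table 6.3.2.1: the pneumonitis row calls for corticosteroid; the diarrhoea/colitis row covers hold or stop, monitoring, consultation and fluids, with no corticosteroid instruction.
- Section 6.3.2.2, closing provision: corticosteroid after discussion with the coordinating committee, but only for toxicities not already listed, so not colitis.
- Section 6.5.1: steroids recommended for immune-related events, with no grade or timing; not giving them is not a deviation.
- Section 6.5.3: the steroid restriction exempts events of suspected immunological cause.
- Section 6 (opening) and section 10.1.5: depart from the protocol where following it may be hazardous, and act at once on an adverse event. Both are general.
- Section 6.3.1.1: lenvatinib interrupted for treatment-related Grade 3 and discontinued for Grade 4. Section 6.2.1, item 3: treatment-related Grade 4 non-haematological toxicity ends protocol treatment. Neither addresses corticosteroid.

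None gives a colitis-specific start earlier than one week at Grade 3–4.

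**The case against.** The strongest reply is that the governing detail has not been seen. The section calls its therapies examples and refers to a guidance document that may give the correct Grade 3–4 start. Sections 6, 6.5.1 and 10.1.5 also push toward prompt action, and hold/stop rules, fluids, the perforation check and specialist review are not tied to the one-week wait. This stands as a limit on how much care would really be delayed, and it means only corticosteroid is affected. It does not correct the sentence.

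A second reply is that the two sentences form a ladder: oral corticosteroid after 3 days for Grade 2 or worse, then intravenous treatment after a week. The error would then be a missing greater-than-or-equal sign in the first sentence. This is possible, but the literal text does not say it, and the preceding sentence does use that sign. A fix that ties Grade 3–4 to a start no later than the Grade 2 trigger deals with both readings.

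Third, colitis also differs from the other entries at Grade 2, where it alone has a persistence condition, so the one-in-six count does not by itself prove an error. That is fair. The finding rests on the 3-day against 7-day inversion; the count only shows that the section offers no parallel for it.

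Finally, prompt corticosteroid before infection or lenvatinib toxicity is excluded is a clinical choice that the protocol does not state for colitis. This is a real cost of the fix and is named there.

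**Conclusion.** The concern holds. As written, the rule starts corticosteroid later at Grade 3–4 than at Grade 2, by 4 days if the week runs from onset of diarrhoea and by 4 to 7 days if it runs from reaching Grade 3–4. It affects patients who reach Grade 3–4 within 3 days. How many that would be cannot be estimated, because the documents give no rate of Grade 3–4 colitis for this combination.

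The conclusion assumes that the sentence is read literally and that the cited guidance document does not override it. Whether the longer wait is a drafting slip or intended cannot be told from the text. This is a safety instruction that should be corrected. The grade-based safeguards and the example status keep it from ranking higher.

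**What to change.** In section 6.3.2.2, remove the one-week condition from the Grade 3–4 sentence and state the start. Suggested content: for Grade 3 or 4 diarrhoea/colitis suspected to be immune-related, give corticosteroid promptly (intravenous, then high-dose oral), in any case no later than the Grade 2 trigger, while infection and lenvatinib toxicity are being excluded. Check both triggers against the guidance document that the section cites. If the longer wait at Grade 3–4 is intended, give the reason in the section.

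The change is one sentence and adds no visits, procedures or patients. The downside is small: some patients whose diarrhoea proves infectious or lenvatinib-related may receive corticosteroid earlier than they otherwise would.

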6.4. Special instructions for subjects

The attending physician and trial collaborators will instruct the subjects on the methods of lenvatinib and pembrolizmab administration and on observing the following matters. When administered on an outpatient basis, a thorough interview and investigation will be carried out regarding the state of lenvatinib administration (e.g., the collection of untaken lenvatinib [i.e., the investigational drug]), and the results will be recorded on a CRF.

6.5. Concomitant and Supportive Therapies

When subjects are undergoing post treatments, describe all the combination drugs and treatments that have been used during the period from start of administration until termination of the follow-up observation period (30 days after the final administration; in cases of undergoing of post treatments, until the day before the post treatments) in the CRFs. It is unnecessary to describe the agents that have been used for the purpose of various examinations/diagnoses in the CRFs, except for cases where the use of such agents is necessary for judging the causality of adverse events.

6.5.1. Recommended combination therapy/supportive therapy

The combination and supportive therapies listed below are recommended.

Nonadministration of the therapies will not be considered a deviation from the protocol.

- 1) Antiemetic agents/fluid replacement: For severe nausea and vomiting that impedes the continuation of oral therapy, the appropriate treatment will be administered using antiemetic agents or fluid replacement.
- 2) Antidiarrheal drugs.
- 3) Antifebrile agent, analgesics, and steroids will be administered for immune-related events.

6.5.2. Allowable combination therapy/supportive therapy

When zoledronic acid and denosumab are administered for bone metastasis before enrollment, such medications can be continued.

6.5.3. Unallowable combination therapy/supportive therapy

Except when required for the treatment of adverse events, safety, and ethical reasons, the concurrent use of the agents listed below shall not be permitted.

- 1) Other anticancer drugs
- 2) Other investigational drugs
- 3) Live vaccines administered <30 days before the initiation of treatment with the investigational drug and during the trial period. Examples of live vaccines are as follows (however, the list is not exhaustive): measles, mumps, rubella, chicken pox/herpes zoster, yellow fever, rabies*, BCG for tuberculosis, and typhoid vaccines*. Inoculation with inactive vaccines (e.g., seasonal influenza vaccines) is permitted; however, the intranasal administration of attenuated influenza vaccines (e.g., Flu-Mist®) is prohibited. (*In Japan, live vaccines are not approved).
- 4) Systemic glucocorticoids for purposes other than treating symptoms caused by notable events with a suspected immunological etiology. Upon deliberation with the trial coordinating committee, the use of corticosteroids may be permitted according to the physiological dose required to alleviate symptoms (e.g., to control symptoms of acute asthma).

Except when required for the treatment of adverse events, safety, and ethical reasons, the concurrent use of the drugs listed below is not permitted. However, use of these drugs to treat adverse events will not be considered a deviation from the protocol.

- 5) Other treatments that affect the evaluation of safety and efficacy (e.g., surgical treatment, radiotherapy, thermotherapy, immunotherapy, hormone therapy, and antibody therapy).

6.6. Subsequent Treatment

There will be no subsequent treatment for patients following the termination of the stipulated treatment protocol.

7. INFORMATION ON THE INVESTIGATIONAL DRUGS

7.1. Drug Information on Lenvatinib

Study drug	Lenvatinib
Dosage form	Capsule
Manufacturer	Eisai
Content	Capsule 4mg:This product contains 4.90 mg of lenvatinib mesilate in one capsule (4 mg as lenvatinib) Capsule 10mg:This product contains 12.25 mg of lenvatinib mesilate in one capsule (10 mg as lenvatinib)
Administration method	Oral
Expiration date	See the Procedures for Study Drug Management
Labelling	The outer box shows the content, storage method, and name, job title and address of the coordinating investigator, and indicates "For clinical study." The job title of the coordinating investigator shown on the outer box should be that at the start of the study, and changes to the job title, if any, should not be reflected on the label of the outer box.

Lenvatinib will be supplied by Eisai, the investigational drug supplier, free of charge. The manufacturing records and records of quality tests of the study drug will be also provided by the investigational drug supplier.

